E.3.b. Effectiveness Measure for Aim 3: In addition to conducting a comprehensive examination of costs, we will systematically examine these costs in the context of the intervention's societal benefits by conducting a formal cost-effectiveness analysis. The cost-effectiveness analysis will employ quality-adjusted life years (QALYs) as the primary measure of societal benefits. We will capture QALY over the course of 2 years using the Health Utilities Index, v.2/3 (HUI-2/3). HUI-2/3 is a utility measurement instrument that consists of 15 items that capture 8 attributes of health-related QoL: vision, hearing, speech, ambulation, dexterity, emotion, cognition, and pain.

The scoring algorithm will be obtained from Health Utilities, Inc. and is based on Canadian health preference weights. Utility scores from this instrument range from 0-1, with a higher score indicating better quality-adjusted life. Previous research has shown that the HUI-3 has consistent validity in people with glaucoma, diabetic retinopathy, and cataracts. QALY will be measured as the amount of utility gained or lost over each year of the program.

E.3.c. Incremental Cost-Effectiveness Ratio: The primary cost-effectiveness measure will be defined as the incremental difference between cost of the enhanced intervention and usual care, divided by the difference in health utility-Incremental Cost Effective Ratio (ICER). The ICER thus will indicate the additional costs to bring about one additional unit of benefit (QALY) from the enhanced intervention compared to usual care. The

reference case, which will be defined as usual care. The ICER obtained will be compared to acceptable thresholds of \$50,000 to \$100,000-QALY. A secondary measure will be cost per diagnosis made.

E.3.d. Sensitivity Analysis for Aim 3: To account for uncertainty in our primary ICER, cost and effectiveness data will be entered into a decision analytic model. This is particularly important since the study will be powered based on the primary outcome, not the cost-effectiveness measure. Sensitivity analyses will ensure robustness of the ICER. Both univariate sensitivity analysis (whereby 1 variable is changed at a time and impact on the ICER will be examined), and probabilistic sensitivity analysis (PSA), whereby all relevant variables are simultaneously modified within reasonable ranges will be conducted. Sensitivity analyses will include those variables where we anticipate “real world” uncertainty.

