The PSA will consist of a Monte Carlo simulation model based on estimated distributions for each variable in the model, with each distribution based on the mean and standard deviation of all probabilities, costs, and effectiveness measures. If the standard deviation of a variable is not available, it will be assumed to be 10% of the mean. The simulation will consist of 10,000 random iterations, with the goal of determining the likelihood that the enhanced intervention is cost-effective compared to usual care. The PSA will be performed using the TreeAge Pro software program (Williamstown, MA). Since the trial employs a time horizon of >1 year, discounting future costs and benefits will be performed at a rate of 3% each year beyond the first.

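### Aim 3 words the QALY and the ICER denominator without multiplying utility by time, so the ratio is not pinned down as a cost per QALY

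*Combined protocol and SAP*

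**What the plan says.** Section E.3.b chooses the measure of benefit: "The cost-effectiveness analysis will employ quality-adjusted life years (QALYs) as the primary measure of societal benefits". The instrument is the HUI-2/3, the horizon for QALYs is 2 years, and utility is scored from 0 to 1. The section then gives its only working definition: "QALY will be measured as the amount of utility gained or lost over each year of the program".

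Section E.3.c builds the ratio. The cost difference between the enhanced intervention and usual care is "divided by the difference in health utility-Incremental Cost Effective Ratio (ICER"). The next sentence interprets the result as the "additional costs to bring about one additional unit of benefit (QALY) from the enhanced intervention compared to usual care". The ratio is then judged against thresholds of $50,000 to $100,000 per QALY.

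Section E.3.d adds that "discounting future costs and benefits will be performed at a rate of 3% each year beyond the first".

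No section gives an area-under-the-curve or other time-weighting rule, an adjustment for baseline utility, or a rule for how deaths enter the QALY. The HUI has no row in Table 5 and is not in the closeout-visit list in C.4.a, so its measurement times are not stated either.

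**The concern.** A utility is a score at a moment. A QALY is that score multiplied by the years for which it is held. The two sentences that say how the denominator is obtained (the E.3.b definition and the E.3.c ratio) use utility gained or lost and a difference in utility. Neither contains a duration.

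If an analyst follows the words, each patient's result is the change in utility over year 1 plus the change over year 2. The middle value cancels and only end minus start remains. How long a benefit was held then has no influence. A patient steady at 0.80 for two years would contribute 0 under this rule, against 0.80 × 2 = 1.60 QALYs by area.

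At stake is Hypothesis 3, which is judged against cost-effectiveness thresholds. A ratio with end-minus-start utility below the line is in dollars per utility point, and per-QALY thresholds do not apply to it. The sensitivity analyses in E.3.d take effectiveness data as an input. If those data carried the same definition, varying them would not reveal the problem.

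**Working it through.** The plan states no utility, QALY or ICER value, so there is no figure to reproduce.

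**Inputs from the documents.** 2-year QALY horizon, HUI-2/3, utility scale 0 to 1 (E.3.b); thresholds $50,000 to $100,000 per QALY (E.3.c); 3% discounting beyond the first year (E.3.d).

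**Assumptions, because the documents give none.** HUI measured at years 0, 1 and 2; usual care flat at 0.80; equal baselines; incremental cost $1,000 per patient.

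**Formulas.** Let u0, u1, u2 be the utilities at years 0, 1, 2, and g0, g1, g2 the gains over usual care, with g0 = 0.

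- Literal rule: (u1 − u0) + (u2 − u1) = u2 − u0. The between-arm difference is g2.
- Area by trapezoid: (u0 + u1)/2 + (u1 + u2)/2. The between-arm difference is g1/2 + (g1 + g2)/2 = g1 + g2/2.

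**Results, undiscounted.**

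| Gain at years 0/1/2 | Literal (g2) | Area (g1 + g2/2) | Literal ÷ area | ICER literal | ICER area |
|---|---|---|---|---|---|
| Linear 0/0.02/0.04 | 0.040 | 0.02 + 0.02 = 0.040 | 1.0 | $25,000 | $25,000 |
| Sustained 0/0.04/0.04 | 0.040 | 0.04 + 0.02 = 0.060 | 0.67 | $25,000 | $16,667 |
| Late 0/0/0.04 | 0.040 | 0 + 0.02 = 0.020 | 2.0 | $25,000 | $50,000 |
| Partly lost 0/0.04/0.02 | 0.020 | 0.04 + 0.01 = 0.050 | 0.4 | $50,000 | $20,000 |
| Transient 0/0.04/0 | 0 | 0.04 + 0 = 0.040 | 0 | undefined | $25,000 |

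**With discounting** (year 2 divided by 1.03), literal vs area: linear 0.0394 vs 0.0391; sustained 0.0400 vs 0.0588; late 0.0388 vs 0.0194; partly lost 0.0206 vs 0.0491. For the transient gain the literal value is 0.04 − 0.04/1.03 = 0.0012, against 0.0394 by area. The pattern does not change.

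**Can the threshold verdict change?** Take an assumed incremental cost of $3,000. For the late gain, the literal ICER is 3,000/0.040 = $75,000 and the area ICER is 3,000/0.020 = $150,000. For the partly lost gain, they are 3,000/0.020 = $150,000 and 3,000/0.050 = $60,000. The verdict at $100,000 changes in both cases, in opposite directions.

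**When the two rules agree.** They agree under linear divergence, as in the first row. They also agree if the HUI is taken only at baseline and 2 years: the trapezoid is then (0 + g2)/2 × 2 = g2.

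**Baseline imbalance.** Suppose the intervention arm sits 0.02 higher throughout and nobody changes. Raw area gives 0.02 × 2 = 0.040 QALYs. The change-score rule gives 0, and so does the area of change from baseline.

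**The case against.** The strongest reply is that the E.3.b sentence is loose wording for QALYs gained or lost during each year. The context supports this: QALYs are named as the measure of benefit, E.3.c calls the unit a QALY, the thresholds are per QALY, and yearly discounting suits a quantity that accrues year by year. If the sentence means time-weighted change from baseline, the between-arm difference equals the area difference whenever baseline utilities are equal, and the denominator is right. This stands. A reader might infer that the plan has committed itself to a wrong denominator; the documents do not support that, only that their wording permits one.

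A reader might also infer a direction, for instance that the ICER will be overstated. The documents do not support that either. A sustained gain makes the literal ICER too high, a late gain makes it too low, and a linear gain leaves it unchanged. With no HUI schedule, even the existence of an intermediate measurement is an assumption.

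A third inference would be that chance differences in baseline utility pass into the QALY as E.3.b words it. They do not when the rule is a change score, because baseline is subtracted. The problem belongs to unadjusted area under the curve, or to a raw utility difference as in E.3.c.

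What the reply does not remove is that both working statements omit time, and that the primary economic ratio depends on which reading the analyst adopts.

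**Conclusion.** The point holds as a wording and specification fault with real consequences under one natural reading. As written, E.3.b and E.3.c do not define a QALY. Taken literally, they give end-minus-start utility, which is generally not comparable with the stated thresholds.

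In the assumed undiscounted examples the literal denominator is 0 to 2 times the area value. The error can be nil, can go either way, and can leave the ratio undefined. These figures rest on invented utility paths, annual HUI measurement and equal baselines; they show what is possible, not what to expect. The threshold reversals also depend on the assumed $3,000.

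The consequence is confined to Aim 3. The Aim 1 and Aim 2 analyses and the Aim 2 power calculation do not use the HUI. E.3.d itself says that the study is not powered on the cost-effectiveness measure. The point is worth correcting before the economic analysis, but it does not threaten the trial's primary result.

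**What to change.** - In E.3.b, define each patient's QALYs as the area under the HUI utility curve, by trapezoid between stated measurement times, discounted as in E.3.d. State how deaths enter the calculation.
- Add the HUI and its time points to Table 5.
- In E.3.c, make the denominator the difference in mean QALYs between arms.
- Estimate that difference by regression adjusting for baseline HUI utility. Unadjusted area carries baseline imbalance into the result, which a change score does not. The adjustment matters more if the two sites assigned wholesale to one arm (C.7.c) enter the comparison, since imbalance there need not be due to chance.

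The cost is a few sentences in E.3, a row in Table 5 and slightly more analysis work. Whether the data already planned suffice cannot be told from the documents, because the HUI schedule is missing. If the HUI is taken only at baseline and 2 years, the area can still be computed, but it rests on assuming a straight line between the two measurements.

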#### **F: Aim 4: Replication, Dissemination and Transition Plan**

Wills Eye and its partners are very eager to share insights, successes, progress, and barriers with key stakeholders, including public health practitioners, academic researchers, primary care providers, governmental agencies, private organizations, and patients. Under the leadership of Wills Eye Hospital Investigators, and working with Westat and the CDC, Wills Eye will disseminate and translate our interventions via the internet, free of charge, for implementation in communities across the nation.

We aim to build a capacity to develop a sustainable intervention that can be freely shared and implemented in additional communities in the following ways:

- Provide training to public health and academic researchers, study staff, FQHC directors, PCPs, ocular technicians, and eye care specialists to enable them to apply best practices to their own settings to address vision-health disparities.
- Publish methodology and final research results about all aspects of the project and its impact in peer-reviewed literature for audiences in primary care, diabetes, telemedicine, and eye care.
- Create presentations and exhibit posters at conferences including the American Glaucoma Society, American Academy of Ophthalmology, American Public Health Association, American Academy of Family Physicians, American Diabetes Association, and National Association of Community Health Centers.
- Disseminate information about this project and its impact through the Wills Eye website ([www.willseye.org](http://www.willseye.org)) and other Wills Eye electronic and print materials, such as webinars, chat rooms, pod casts, and list serves.
- Present information about our project and its impact on vision and eye care to the broader Philadelphia community at meetings and conferences and through local publications.
- Provide information about this project to Philadelphia’s public health officials.
- Share project outcomes regarding the FQHC with HRSA and other policy makers.
- Develop and design an inventory of assessment and outcome measures to guide replication and expansion of the teleophthalmology methods and the Patient-Navigation Training Manual (Appendix I).
- Create electronic handbooks for professional that define setting, partners, scope, intensity, reporting, and outcome measures for detecting and managing eye disease and functional vision loss.

Dissemination plan will begin in Year 2. Methodology papers will be written on the baseline population. We will share research findings through websites, webinars, conference presentations, reports/fact sheets, peer-reviewed journal articles, and electronic manuals. All products and tools will define the setting, partners, scope, intensity, reporting, and outcome measures. Using the *RE-AIM Framework* described in Section D, we will focus on implementation and maintenance. Our dissemination plan aims to ensure that our education materials, data capturing tools, electronic handbook, and patient navigator/social worker protocols will be publicly available. The intervention has sufficient rigor and fidelity to be replicated and implemented in communities across the nation.

In collaboration with the Tel-Aviv Medical Center and the Bar-Ilan University (Israel), we plan to develop a deep learning algorithm to detect glaucoma using the optic disk and fundus photography obtained at Visit 1, as well as demographic and clinical data from visits 1 and 2. A password protected hard drive with the de-identified data (fundus photos and clinical information) will be shared with Drs. [name] at the Tel-Aviv Medical Center and [name] at Bar-Ilan University. The deidentified data will remain stored on secure servers protected by two passwords at the Tel-Aviv Medical Center and at the Bar-Ilan University. HIPAA compliance will be achieved through the Safe Harbor method.

Our aim is to develop a software for detection of glaucoma suspicious discs, based on deep-learning algorithm. The software will be available for research purposes for investigators from other institutions worldwide by using cloud-based open-access platform. Researchers will be able to upload images and evaluate the ability of the suggested software to detect suspicious discs, free of charge. The end-user will be able to upload color fundus images to the website. The images will be sent to our cloud servers, where each image will be processed and a glaucoma detection report will be sent back to the user. In case the user does not approve sharing the images they will not be saved in our database. Otherwise, these images will help us improve the proposed algorithm and expand our database.

## **G: Study Timeline, Monitoring, and Community Advisory Board**

**G.1.a. Study Timeline and Milestones:** We will implement and evaluate the project tasks and measurable milestones according to the timeline in Appendix K. We have identified realistic milestones including baseline and follow-up assessments, data collection, data management, and data analysis for the 5-year period. Beginning September 30, 2014, we will initiate IRB protocol submissions at Wills Eye and the partner institutions including Public Health Management Corporation, Philadelphia Department of Public Health, Health Federation of Philadelphia, and Temple Physicians, Inc. This will allow adequate time from the funding notification to obtain IRB approval. After IRB approval, patient enrollment will begin 1/1/15 and last 15 months. Table 8 describes the process measures.

**G.1.b. Independent Study Oversight: Data Safety and Monitoring Board (DSMB):** This study will utilize a DSMB that has been established specifically for this CDC project. This group will assure that protocols are followed properly, case reports match the source documents, inclusion and exclusion criteria are followed, and all subjects are consented properly. In addition, the DSMB will review safety data after we have enrolled subjects at all sites.

The DSMB will meet annually and develop a monitoring plan for transmitting reports to the IRB. The report will provide individual findings, overall safety assessment, and recommendations. The summary report will include the study's protocol, participant enrollment, procedures, and data quality. The report will also inform study investigators of the DSMB members' conclusions with respect to the study's progress or need for modification of the protocol. Meetings will also allow investigators and the DSMB to review data including

VFQ results, rates of follow-up eye care, sensitivity analysis of glaucoma detection using telemedicine images vs. comprehensive glaucoma exam, recruitment, and enrollment reports, and satisfaction questionnaire results.

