#### **C.4. Research Design and Methods**

**C.4.a: Project Overview:** The Wills Eye Glaucoma Research Center will conduct a 5-year prospective, randomized controlled trial to evaluate an innovative, community intervention using posterior fundus photographs of the optic nerve and macula to improve access and utilization of eye care to detect, treat, and manage high-risk patients with previously undiagnosed glaucoma, glaucoma suspect, and other eye diseases. L. [name]; [name]; and [name], RD, will lead the research study.

Our diverse targeted, at-risk population includes African Americans, Hispanics, and Asians over age 40; other older adults (aged 65+); individuals over age 40 with a family history of glaucoma and/or with diabetes. Approximately 1250 patients will be recruited from geographically diverse locations across Philadelphia and Chester counties, with the help of our community partners. **Phase 1** will consist of detecting eye disease in 7

primary care offices and 10 FQHC using telemedicine (Visit 1), followed by a comprehensive eye exam by a Wills glaucoma specialist in the same setting to confirm the diagnosis (Visit 2). Based on preliminary data, 30% of patients (approximately 750) will have abnormal optic nerve and/or macula images. The predictive accuracy of the optic nerve images to detect glaucoma and glaucoma suspect as confirmed by the comprehensive eye exam will be evaluated.

**Phase 2** will involve consenting, enrolling, and randomizing 374 patients to either the usual care group (n=187) or the enhanced intervention group (n=187). The enhanced intervention will consist of using patient navigators and a social worker to reduce barriers to follow-up eye care. **Phase 3** will consist of following patients proximally (6 months) and distally (3 years) while they attend appointments with a local, eye care provider (Visits 3-7). Adherence to follow-up recommendations for eye care will be the primary outcome measure. A comprehensive cost study to estimate the intervention costs and cost-effectiveness of detecting eye diseases and vision impairment in a high-risk population will also be conducted. Protocols, materials, outcomes, and results will be disseminated to other communities in order to expand detection of glaucoma, other eye diseases, and visual impairment, and to further refine these approaches to successfully scale the program up to a national level.

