C.8. Patient Navigation Protocol (Appendix I): The use of patient navigators and social workers has proven successful in cancer care programs, showing higher rates of follow-up care, while increasing patient satisfaction and decreasing anxiety. Patient navigation shows promise as the missing link between available services and healthcare delivery to vulnerable populations. By educating and guiding patients, navigators can lessen the disparities among racial/ethnic groups at risk for eye disease. Our study staff, project managers, ocular technicians, and research assistants have been trained to serve as patient navigators. Their responsibilities will include: phoning patients to schedule appointments; confirming appointments by mailings, emails and/or text messaging; arranging transportation through Customized Community Transportation (CCT) and Philadelphia Paratransit Service; and scheduling trained medical interpreters.

Wills Eye ocular technicians will also assist patients in the enhanced intervention group across 17 sites with medication refills and obtaining free medications from pharmaceutical companies. Our patient navigators can identify cultural and language differences and are aware of health literacy issues. We will also provide multiple outreach strategies as additional barriers are identified. Results will be discussed at our weekly research team meetings, quarterly meetings with each partner, and annual meetings with our Advisory Board.

C.8.a. Identifying Barriers to Follow-up Using Social Workers: Research shows that individuals at high risk for glaucoma are not likely to participate in screening programs or ongoing follow-up with an ophthalmologist in an office-based setting. Appendix J describes how innovative approaches to identifying and remediating barriers have been accomplished in our current CDC glaucoma detection program and can be tested, refined, and implemented in this proposed study (Section C.2.a). Educational materials may help non-adherent patients to understand the benefits of taking glaucoma medications regularly.

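### The DSMB's safety review waits until all 17 sites have enrolled, so the slowest site sets its date and it probably comes after most Visit 1 exams

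*Combined protocol and SAP*

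**What the plan says.** G.1.b sets up a DSMB specifically for this project. Its duties on protocol adherence, source documents, eligibility and consent carry no timing condition. Safety data do: "In addition, the DSMB will review safety data after we have enrolled subjects at all sites". On frequency: "The DSMB will meet annually and develop a monitoring plan for transmitting reports to the IRB". No date is given for the first meeting.

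G.1.a gives the enrolment period: "After IRB approval, patient enrollment will begin 1/1/15 and last 15 months". C.4.a lists 7 primary care offices and 10 FQHCs, and C.8 confirms the total: "Wills Eye ocular technicians will also assist patients in the enhanced intervention group across 17 sites". The order in which sites open is not stated.

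C.5.c places the plan's acute findings at Visit 1. IOP above 30, 35 or 40 mm Hg in either eye calls for an ophthalmology visit within 2 weeks, 1 week or 1 day respectively. Those patients skip Visit 2 and, if they continue, consent to the second part and are randomised at Visit 1. Eye emergencies such as a detached retina are acted on by telephone at once.

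G.1.b requires the board's report to assess safety overall. The data it names for meetings are VFQ results, follow-up rates, detection accuracy, recruitment and enrolment, and satisfaction. The list is introduced as non-exhaustive.

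**The concern.** The condition is tied neither to calendar time nor to the number of patients examined. It is met only when the last of 17 sites has enrolled, and the review then waits for the next annual meeting. The urgent-referral route is used mainly at Visit 1, so it is busiest during the 15 months of enrolment. The board can recommend protocol changes, but a recommendation about Visit 1 helps only patients not yet screened.

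The realistic failure is systematic: for example, patients at one site who are referred with high pressure but not seen within the stated window. The plan's own experience shows that referral does not ensure attendance. In the network study (C.3.c), 35% of patients with abnormal results reported seeing an eye-care provider by three months. Those were not urgent referrals, so the figure shows only that such a failure is plausible.

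The listed measures would not show it directly. The nearest row of Table 8 counts follow-up intervals recommended from Visit 2 onward. It has no 1-day category and does not record whether the patient was seen in time.

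**Working it through.** **Inputs from the documents**
- Sites: 7 + 10 = 17 (C.4.a), which reproduces the figure in C.8.
- Enrolment: 15 months from 1/1/15 (G.1.a).
- DSMB meetings: every 12 months (G.1.b).
- Visit 1 total: about 1,250 (C.4.a) or 2,500 (D.1.a). The two need reconciling, but the percentages below do not depend on them.
- Visit 1 throughput: about 25 patients per session (C.5.c).

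**Assumptions**
- Visit 1 exams accrue evenly over the 15 months.
- The first meeting is at month 9 (one year after IRB submissions begin on 30 September 2014) or month 12 (one year after first enrolment).

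**Formulas**
- First safety review = first annual meeting on or after the month the last site enrols.
- Share past Visit 1 = min(1, review month / 15).

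**When the last site might enrol**
- Rotation through the sites, one session each: 1,250 / 25 = 50 sessions, so 17/50 × 15 = month 5.1. With 2,500, there are 100 sessions, so 17/100 × 15 = month 2.6.
- Sites opened evenly, one after another: 16/17 × 15 = month 14.1.

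**Results**

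| First meeting | Last site enrols | First safety review | Share past Visit 1 |
|---|---|---|---|
| Month 9 | by month 9 | month 9 | 9/15 = 60% (750 of 1,250; 1,500 of 2,500) |
| Month 12 | by month 12 | month 12 | 12/15 = 80% (1,000 of 1,250; 2,000 of 2,500) |
| Month 9 | after month 9, e.g. 14.1 | month 21 | 100%, 21 − 15 = 6 months after enrolment closes |
| Month 12 | after month 12, e.g. 14.1 | month 24 | 100%, 24 − 15 = 9 months after enrolment closes |

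**Sensitivity.** A grid over every first-meeting month (0–12) and last-site month (0–15), weighted equally, gives an average share past Visit 1 of 79%. At least half have passed Visit 1 in 84% of combinations, and the review falls at or after month 15 in about 40%. If enrolment is read as Phase 2 consent, taken 1–2 months after Visit 1, the average rises to 83–86% and the last figure to 47–54%. Equal weighting describes the range; it is not a forecast.

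**Comparison.** A review fixed at month 6 would come at 6/15 = 40% of Visit 1 exams (500 of 1,250; 1,000 of 2,500).

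**The case against.** The strongest reply is that oversight does not rest on this one sentence. The board's duty to check that the protocol is followed has no all-sites condition, and the urgent windows are protocol rules. Follow-up rates are on its meeting list. For each elevated pressure a Wills ophthalmologist calls a local provider, and in an emergency the patient and PCP are telephoned at once (C.5.c). The research team meets weekly and the partners quarterly (C.8), and CDC calls are monthly (G.1.d). Visit 1 consists of undilated photography, acuity and rebound tonometry, and the randomised intervention is navigation and social work. High pressure and retinal detachment are existing disease found by screening, not harms of the study. All of this stands, and it limits the severity.

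A reader might go further than the text allows in four ways:
- **That safety review necessarily follows the last Visit 1.** This needs a site to enrol after the meeting held during enrolment, and nothing in the documents says one will. With rotation, all sites could be open by month 2.6 or 5.1.
- **That a referral failure could not be found or corrected during screening.** The routes above could find it. They are largely run by the study team and funder, however, and the board's own protocol checks also wait for an annual meeting.
- **That no safety data are collected.** IOP and visual acuity are recorded (Tables 5 and 7), and E.1.c records exam dates and kept or missed visits. What is lacking is a stated safety listing for the board.
- **That a site which never enrols blocks review for good.** That is a strained reading, since such a site has no subjects to review.

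Appendix K and the board's monitoring plan are not in the supplied text and may give dates or content.

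**Conclusion.** The concern holds as a matter of timing. G.1.b defers only the review of safety data, and defers it to an event that the slowest of 17 sites controls. On the two assumed meeting dates, the first independent safety review comes at about 60% or 80% of Visit 1 exams, or at 100% if a site enrols after the meeting held during enrolment. These figures rest on even accrual and on meeting dates that the documents do not give. A meeting before month 7.5 (half of 15) with every site already open would bring the share below half.

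The consequence is late independent detection of a systematic failure in urgent referral, not late care for any individual. With low-risk procedures and several other lines of oversight, this is worth changing but of modest severity. The absence of named safety counts would by itself be only missing detail; the point rests on the all-sites condition.

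**What to change.** In G.1.b, delete the all-sites condition. State that the first safety review takes place at a fixed early point whatever the number of open sites, for example 6 months after first enrolment or after a set number of Visit 1 exams, and then at each annual meeting. Give the date of the first DSMB meeting relative to the start of enrolment.

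For that review, compile by site from records already held:
- emergencies found at Visits 1 and 2;
- urgent-IOP referrals, by the plan's existing categories;
- the number of those patients seen within the plan's stated windows.

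The cost is one revised sentence, a short listing, and one extra teleconference or circulated report for a board that already exists. No clinical threshold or referral window changes.
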